Various studies have evaluated the outcomes of different barbed suture devices, however there are no reports assessing the length of closure times using STRATAFIX (Ethicon, Johnson and Johnson, Somerville, New Jersey) Knotless Tissue Control Devices during deep closure in total hip arthroplasty. Stephens et al. [5] performed a prospective randomized study of 500 total knee arthroplasty patients who received either barbed suture (250) or conventional sutures (250) for deep closure of the surgical wound. The mean operating time was significantly shorter in the barbed group as compared to conventional group (64.3 vs 68.1 minutes, $p=<0.001$). In a study of 80 TKA (61 barbed, 19 conventional deep sutures) and 54 THA patients (37 barbed, 17 conventional deep sutures), Smith et al. [6] found significantly shorter closure time in the barbed suture group (16.78 vs. 26.5 minutes, $p<0.001$). One study reports one the use of Stratfix suture for intracorporeal suturing in myomectomy. Giampaolino et al. [7] performed a prospective randomized study on 47 patients and evaluated the mean operative time for

laparoscopic posterior myomectomy using Stratafix or conventional suture for intracorporeal suturing. There was a significant decrease in mean operative time associated with use of Stratafix suture as compared to conventional suture (66.3 vs 73 minutes, p=0.005).

This prospective randomized single-center study will examine the outcomes, mainly closure time, of deep closure during total hip arthroplasty using the STRATAFIX Symmetric PDS Plus (Ethicon, Johnson and Johnson, Somerville, New Jersey) barbed suture compared to interrupted VICRYL suture (Ethicon, Johnson and Johnson, Somerville, New Jersey).

Study Design:

In this prospective study examining the deep closure during total hip arthroplasty, active subjects will receive the STRATAFIX Symmetric PDS Plus (Ethicon, Johnson and Johnson, Somerville, New Jersey) suture while the control subjects will receive interrupted VICRYL suture (Ethicon, Johnson and Johnson, Somerville, New Jersey). Superficial closure will be the standard of care for both groups.

The purpose of this study is to compare end points (see below):

- **The primary endpoint** of the study will be closure time and operative time.
- **Secondary endpoints** will examine: wound complications, costs comparison between the two techniques.

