Post-operatively, patients will be assessed at clinic visits at 6 weeks and 3 months. At these time points, we will assess (**Table 1**):

Table 1.

REQUIRED STUDIES	Pre-Op	Intra-operative	6 week post-op	3 month post-op
Informed Consent	x			
Length of surgery time		x		
Length of closure time		x		
Amount of suture material used		x		
Surgeon experience level		x		
Wound complications			x	x

Methods

- A prospective randomized pilot study

Sample

- 60 subjects for a pilot study

Inclusion Criteria:

1. Males and females, between the ages of 18 to 80 years at the time of signing the informed consent document.
2. Understand and voluntarily sign an informed consent document prior to any study-related assessments/procedures are conducted.
3. Able to adhere to the study visit schedule and other protocol requirements.
4. Able to fluently speak and understand the local language
5. If female, is non-pregnant (negative pregnancy test results at the baseline/randomization visit) and non-lactating.
6. End-stage osteoarthritis patients planning to undergo primary total hip arthroplasty
7. BMI less than 40 kg/m²

Exclusion Criteria:

1. BMI greater than or equal to 40 kg/m².
2. History of known bleeding disorder.
3. History of medical co-morbidity that may result in poor wound healing (i.e. diabetes mellitus, peripheral vascular disease).
4. Patients <18 or >80 years of age.
5. Patients who are prisoners.
6. Mentally unable to sign informed consent.
7. Has an uncontrolled illness that, in the opinion of the investigator, is likely to cause the patient to be withdrawn from the trial or would otherwise interfere with interpreting the results of the study.

Screening and Recruitment: Informed Consent

Informed consent will be obtained by one of the study coordinators/co-investigators during a clinical visit prior to procedure in the privacy of an examination room or an office. Patients will be informed about the study and inquired about their interest to participate. A consent document will be given and key parts of the research study will be explained in lay-terms to the patient to ensure full understanding. Any questions regarding the research study

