will be answered at that time. It will be emphasized that participation is voluntary. Those patients who are willing to participate will be asked to sign the consent document along with the consenting researcher. A signed copy of the consent document will be handed to the patient while another copy is kept in their study file.

In the event that an approach prior to the day of surgery is not feasible, same day of procedure consenting will be attempted. Patients will be contacted by telephone (see phone script), and those interested in participating in the study will be informed about what is involved, the follow-up visit, and that participation in the study is strictly voluntary, and will not affect the scheduling of their upcoming surgery. If the patient is interested in participating, the patient can be either mailed or emailed a copy of the informed consent form, and then arrangements will be made to complete the informed consent process prior to the patient being taken back into the preoperative area on the day of surgery. The patient will be asked to come to the hospital on the day of surgery earlier than the time they were told to arrive by surgical scheduling in order to make sure there will be adequate time to discuss the study, including what is involved, risks, benefits, and alternatives. We do not believe that an eventual approach on the same day of procedure would represent an added stress for the patient or delay the start of the procedure. Similar to obtaining informed consent prior to the day of procedure, the process will occur in a private setting with ample time to discuss the study's implications, risks, benefits, and alternatives. No procedures or tests will be conducted on the screening visit after consenting the patient.

Randomization procedures:

Patients will be randomized to either arm of the study as follows: sealed envelopes in a random order will be used to place study participants in either the barbed suture arm or in the traditional suture arm of the study. Patients will be randomized in a one to one ratio. At the commencement of each arthroplasty, a random envelope will be drawn which dictated the type of suture to be used, thus blinding the patients to the type of suture they received.

Research Procedure:

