- Cancer: Not related and unexpected within 10 working days from discovery/awareness

b) External Death:

Related/possibly related and unexpected – within 5 working days from discovery/awareness not related whether expected or unexpected – at time of continuing review related/possibly related and expected – at time of continuing review

c) ALL Deaths are also reported at time of continuing review using the AE summary log.

4. Non-serious Adverse events (Internal and External) that are both Related/Possibly related and unexpected are reported on the AE Summary Log at time of continuing review to assess trends.

5. An IRB staff (a qualified, licensed practitioner assigned to this function by the IRB chair and IRB Executive Director) reviews Adverse Event Reports to determine whether they represent Unanticipated Problem Involving Risks to Participants or Others. Events that are assessed, by either the IRB Staff or Investigator, to place subjects or others at a greater risk of harm than was previously known or recognized, or changes the risk/benefit ratio of the study, or

requires a change in the protocol and/or consent document are referred to Full Board for review under Policy #70. Events that do not involve risk to Participants or Others or changes to the informed consent or protocol do not require further review. Investigators are informed of the determination and the IRB file is updated.

6. The AE Summary Log is reviewed by the IRB at the time of continuing review to identify trends in frequency and severity which may impact subject safety.

This study is an Investigator Initiated research trial. Each study site will be considered its own regulatory sponsor and is responsible for internal data monitoring and any study reporting required by ClinicalTrials.gov.

Data Analysis:

Unless otherwise indicated, all testing of statistical significance will be two-sided, and a difference resulting in a p-value of less than or equal to 0.05 will be considered statistically significant. Also, after each analysis, General Linear Models (GLM) will be used to control for possible confounders, including BMI, gender, age and ethnicity.

References:

- [1] A. Sull, S. Inceoglu, A. August, S. Gregorius, and M. D. Wongworawat, “Comparison of Barbed Sutures in Porcine Flexor Tenorrhaphy,” *HAND*, vol. 11, no. 4, pp. 475–478, Dec. 2016.

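### Incision length is neither recorded nor a named covariate, so avoidable noise stays in the closure-time comparison

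*Combined protocol and SAP*

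**What the plan says.** Under Study Design, the primary endpoint "of the study will be closure time and operative time". The intra-operative column of Table 1 holds four items: the duration of surgery, "Length of closure time", the quantity of suture used, and the experience level of the surgeon. Neither incision length nor wound length appears there or anywhere else in the document.

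Data Analysis gives one sentence on adjustment: "General Linear Models (GLM) will be used to control for possible confounders, including BMI, gender, age and ethnicity". The list is open, but incision length is not on it. The same section states that "all testing of statistical significance will be two-sided" and that "a p-value of less than or equal to 0.05 will be considered statistically significant".

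Sample gives "60 subjects for a pilot study". Randomization procedures adds: "Patients will be randomized in a one to one ratio". No blocking or stratification is described. On timing, the same section says: "At the commencement of each arthroplasty, a random envelope will be drawn which dictated the type of suture to be used". The arm can therefore be known before the incision is made.

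Research Procedure and Table 2 describe one posterior approach for all patients. The suture material differs between arms only in the fascia.

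**The concern.** Closure time plausibly rises with the length of the wound. By the plan's own description, the layers above the fascia are closed with interrupted knots in both arms, and so is the fascia in the control arm. The barbed suture runs along the wound from its upper end. A longer wound means more throws in each of these layers. Much of the resulting patient-to-patient variation comes from layers that are treated alike in both arms, while the contrast of interest comes from one layer.

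Nothing collected replaces the measurement. Suture quantity depends on the assigned technique, so adjusting for it would remove part of the effect under study. BMI, gender and age are at best indirect proxies. At stake are the precision of the closure-time estimate and the ability to see whether the arms were alike in wound length. For a pilot, there is also the chance to learn how strongly wound length drives closure time before a larger trial is planned.

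**Working it through.** **Inputs from the documents.** N = 60 (Sample); 1:1 allocation, so n = 30 per arm if the split is exact (Randomization procedures); two-sided alpha 0.05 (Data Analysis). No power, effect size, SD or dropout rate is stated, so the figure of 60 cannot be reproduced.

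**Assumed input.** ρ is the partial correlation of incision length with closure time after the named covariates. The documents give no value; 0.2, 0.3 and 0.5 are shown. The power figures use a normal approximation.

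**Step 1: chance imbalance.** The between-arm difference in mean incision length has SD √(2/30) = 0.258 patient-SDs, with a 95% range of ±1.96 × 0.258 = ±0.51. The probability of an imbalance above 0.3 SD is about 25%, and above 0.5 SD about 5%. An imbalance of 1.96 standard errors shifts the closure-time difference by ρ × 0.51, that is 0.10, 0.15 or 0.25 outcome-SDs.

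**Step 2: detectable difference without the covariate.** At 80% power: (1.960 + 0.842) × 0.258 = 0.723 SD.

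**Step 3: gain from adjustment.** Variance removed = ρ². Equivalent N = 60/(1 − ρ²). Detectable difference = 0.723 × √(1 − ρ²).

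| ρ (assumed) | Variance removed | Equivalent N | Detectable difference (SD), 80% power | Power for 0.723 SD |
|---|---|---|---|---|
| 0 | 0% | 60 | 0.723 | 80.0% |
| 0.2 | 4% | 62.5 | 0.709 | 81.6% |
| 0.3 | 9% | 65.9 | 0.690 | 83.6% |
| 0.5 | 25% | 80.0 | 0.626 | 89.9% |

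**Step 4: price of the covariate.** The table ignores the lost degree of freedom. With one covariate, estimating its slope inflates the expected variance by about 1/(60 − 4) = 1.8%, and slightly more with the other covariates in the model. The net variance factors are 0.96 × 1.018 = 0.977, 0.91 × 1.018 = 0.926 and 0.75 × 1.018 = 0.764, so the net reductions are about 2%, 7% and 24%.

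**Step 5: operative time.** Closure is only one part of the operation. If wound length adds the same minutes to both times, its correlation with operative time shrinks in proportion to the larger SD of operative time. As an illustration, if that SD is twice the closure-time SD (assumed), ρ = 0.5 becomes 0.25. The variance removed is then 6.25% and the equivalent N is 60/(1 − 0.0625) = 64.

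**The case against.** The strongest reply is that the plan contains no error here. Under randomization, a chance imbalance in an unmeasured covariate is already reflected in the standard error. A reader might infer from the omission that the closure-time result would be biased or the test invalid; the documents do not support that. This part of the reply stands in full.

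Several other points also stand, at least in part:

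- A single approach, the BMI limit in the eligibility criteria, and adjustment for BMI, gender and age narrow or partly capture wound size. Only the residual correlation counts, and it may be low.
- A reader might expect equal harm to both primary times. The effect on operative time should be weaker, as Step 5 shows.
- It is tempting to express the loss in minutes and set it against the 3.8-minute operating-time difference (68.1 − 64.3) in the Background section. The documents give no incision-length SD or minutes per centimetre. That difference comes from knee patients, and the cited closure-time difference is 26.5 − 16.78 = 9.72 minutes, in knees and hips combined.
- With the draw at the start of surgery, only the marked line is a safe pre-allocation measure. The wound actually closed may be longer, so the correlation is probably weaker than for the true length. Reporting time or suture use per centimetre closed does not follow from such a mark.
- Table 1 also omits BMI, age, gender and ethnicity, which the analysis uses, so it is not a complete list of the data collected. Even so, no other section mentions incision length.
- The measurement is not wholly irrecoverable: the wound is seen again at 6 weeks and 3 months. A scar length taken then could support a descriptive check, but it is a post-allocation measure and a poor covariate.

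None of this removes the case for a cheap measurement, because an open covariate list cannot make use of a variable that nobody recorded.

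**Conclusion.** The point holds as an inexpensive improvement in precision for closure time. The omission is plain from the text; its cost is not. At a partial correlation of 0.3 or less the gain is small (detectable difference 0.723 SD falling to 0.690 SD at best). At 0.5 it is material (0.626 SD, equivalent to 80 patients). The documents cannot say which applies, and without the measurement the trial could not say either. The conclusion rests on the assumed correlations, an exact 30:30 split, and a marked line that tracks the wound closely enough to be useful. It does not extend to a claim of bias, to an equal effect on operative time, or to any loss stated in minutes.

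**What to change.** Add a row for incision length (cm) to Table 1, measured in every patient before the envelope is opened. Under the present draw at the start of surgery, this means the marked skin incision. Name it in Data Analysis as a pre-specified covariate in the closure-time model, and secondarily in the operative-time model. Surgeon experience, which is already collected but not among the named covariates, could be pre-specified in the closure-time model at the same time.

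The cost is one ruler measurement per patient by staff already present and one degree of freedom in each model. The downside is that a marked line may be extended during surgery, so it is an imperfect proxy for the wound that is closed.

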A standard posterior approach will be performed by the participating surgeons. For the traditional closure (control group), Abductor muscles will be repaired using Ethibond, and the deep fascia will be repaired using interrupted number 1 braided absorbable sutures (Vicryl, Ethicon; Johnson & Johnson, Somerville, NJ). The subcutaneous fat layer will be then closed with simple interrupted knots using number 2-0 braided absorbable sutures (Vicryl), followed by closure of the subcutaneous layer using a number 2-0 monofilament absorbable suture with inverted interrupted knots (Monocryl, Ethicon; Johnson & Johnson) followed by the use of steri-strips and adhesive (See table 2).

For the active arm of the study, wound closure will be performed in this fashion: abductor muscles will be repaired using Ethibond 2-0 (Excel MX69G), and STRATIFIX symmetric PDS Plus #1 will be used to close the fascia. (See Table 2). The subcutaneous fat layer will be then closed with simple interrupted knots using number 2-0 braided absorbable sutures (Vicryl), followed by closure of the subcutaneous layer using a number 2-0 monofilament absorbable suture with inverted interrupted knots (Monocryl, Ethicon; Johnson & Johnson) followed by the use of steri-strips and glue (See table 2).

Closure with the unidirectional barbed suture involves starting at the upper end of the wound and proceeded distally. At the ends of the wounds, the suture is backstitched toward the midpoint for further reinforcement before bringing the needle out through the skin; the suture is then cut flush with the tissue at its free end. With each throw, the leading end of the suture is pulled with only enough tension to engage the barbs with the surrounding tissue, thereby locking the wound edges into approximation. As with the traditional closure and in concordance with our routine protocol, barbed closures were finished with skin steri-strips and adhesive.

Table 2: Suture Type for Closure Following Total Hip Arthroplasty.

Layer	Control Group	Active Group
Muscle	Ethibond 2-0 (Excel MX69G)	Ethibond 2-0 (Excel MX69G)
Fascia	Vicryl #1 (J947H#1)	STRATIFIX (SXPP1A04#1)
Subcutaneous	Vicryl 2.0 (J945H 2-0)	Vicryl 2.0 (J945H 2-0)
Subcuticular	Monocryl 3.0 (Y496H)	Monocryl 3.0 (Y496H)

Skin	Steri-strips, glue (Standard of care)	Steri-strips, glue (Standard of care)
------	---------------------------------------	---------------------------------------

Patient Protection:

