All data collection sheets will be de-identified. All patients will be assigned a study ID. All data collected will be entered into Excel sheet and stored on Cleveland Clinic secure computers. Only members of the study team (listed on the IRB application) will have access to protected health information of patients included in this study.

Safety Monitoring Plan

Procedural safety will be documented in this study through patient and surgeon reported adverse events. AEs will be documented for all cases in this study. An Unanticipated Problem involving risks to participants or others is any event that (1) is unforeseen, (2) caused harm or placed a person at increased risk of harm, and (3) is related to the research procedures.

An Adverse Event (AE) is any untoward or unfavorable medical occurrence, including any abnormal sign (for example, abnormal physical exam or laboratory finding), symptoms, or disease. Adverse events can encompass both physical and psychological harms. An Internal Adverse Event (AE) is an untoward medical occurrence, which occurs to participants in research conducted by Cleveland Clinic and/or Cleveland Clinic is the IRB of record. External Adverse Event (AE) is an untoward medical occurrence experienced by subjects enrolled at other institutions for the same study approved at Cleveland Clinic or a different study using the same study drug/device. A Serious Adverse Event (SAE) is any adverse experience that results in any of the following outcomes:

- Death
- A life-threatening experience
- Inpatient hospitalization or prolongation of existing hospitalization
- A persistent or significant disability/incapacity.
- A congenital anomaly/birth defect

- Important medical events that may not result in death, be life-threatening, or require hospitalization may be considered a serious adverse drug experience when, based upon appropriate medical judgment, they may jeopardize the patient or subject and may require medical or surgical intervention to prevent one of the outcomes listed in this definition.

An Unexpected Adverse Event means any AE not previously known or included in the current Investigator's Brochure, consent form or other risk information.

Related/Possibly Related means there must be reasonable evidence to suggest the event was caused by the drug, device or investigational intervention.

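### No stratification or blocking by surgeon is stated, and surgeon is neither listed for collection nor named in the model, although both primary endpoints are times that depend on the operator

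*Combined protocol and SAP*

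**What the plan says.** All references are to the combined protocol and SAP.

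- **Randomization procedures.** The method is that "sealed envelopes in a random order will be used to place study participants in either the barbed suture arm or in the traditional suture arm". The section adds "Patients will be randomized in a one to one ratio" and "At the commencement of each arthroplasty, a random envelope will be drawn which dictated the type of suture to be used". It mentions no strata and no blocks. It does not say how the sequence is generated or how many envelope sets there are.
- **Research Procedure.** "A standard posterior approach will be performed by the participating surgeons": more than one surgeon, with no number given.
- **Study Design.** The primary endpoint is closure time and operative time.
- **Table 1.** Surgeon experience level is recorded during the operation, with no categories defined. Surgeon identity is not listed.
- **Data Analysis.** General linear models adjust for possible confounders. BMI, gender, age and ethnicity are named; surgeon, experience level and site are not. The list is worded as open-ended.
- **Sample.** "60 subjects for a pilot study".
- **Number of sites.** Background and Significance says "This prospective randomized single-center study will examine the outcomes, mainly closure time, of deep closure during total hip arthroplasty". The Regulatory Sponsor paragraph, repeated just before Data Analysis, says "Each study site will be considered its own regulatory sponsor and is responsible for internal data monitoring". Patient Protection says data are "entered into Excel sheet and stored on Cleveland Clinic secure computers", which names one institution.

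**The concern.** Surgeons differ in how fast they operate and close. If the draw takes no account of who is operating, a slow or fast surgeon can by chance contribute more cases to one arm, and part of the observed suture difference is then a difference between surgeons. With 60 patients this may not average out well.

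The protocol treats the operator as relevant, since it collects experience level, but it uses that information neither in the allocation nor among the named covariates. Because surgeon identity is not listed for collection, adjustment by surgeon afterwards is not assured either. What is at stake is precision in a small trial. Operative time is the more exposed endpoint, because the differences that the protocol cites for it are smaller than the one it cites for closure time.

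**Working it through.** The plan gives no power, effect size, SD or imbalance figure, so there is no stated figure to reproduce. The check asks how uneven the arms can become within a surgeon, and what that does to the arm difference.

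**Inputs.** From the documents: N = 60 and 1:1 allocation, so 30 per arm if exact. Assumed: the number of surgeons S, equal caseloads m = 60/S, and the between-surgeon SD τ.

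**1. Chance of an uneven split.** With a fixed set of 30 + 30 envelopes, one surgeon's count in an arm is hypergeometric (60, 30, m). With simple 1:1 randomization, which the text also permits, it is binomial (m, ½). For one surgeon with 15 cases, a split of 2:1 or worse has probability 0.23 (fixed set) or 0.30 (simple). The chance that at least one surgeon is split 2:1 or worse, from 40,000 simulated allocations, is:

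| Surgeons × cases | Fixed 30:30 | Simple 1:1 |
|---|---|---|
| 2 × 30 | 2% | 19% |
| 3 × 20 | 13% | 31% |
| 4 × 15 | 58% | 76% |
| 6 × 10 | 84% | 92% |

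Unequal caseloads raise the risk: three surgeons with 30, 20 and 10 cases give 33% under the fixed set, against 13% with equal caseloads.

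**2. Error added to the arm difference.** Let surgeon s have mean shift u_s (SD τ) and x_s of m cases in the barbed arm. The contribution to the arm difference is

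d = Σ u_s(2x_s − m)/30.

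Under the fixed set, Var(x_s) = (m/4)(60 − m)/59. Summing over S = 60/m surgeons gives

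Var(d) = S × τ² × 4Var(x_s)/900 = τ²(60 − m)/885.

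- S = 2: √(30/885) = 0.18τ
- S = 3: √(40/885) = 0.21τ
- S = 4: √(45/885) = 0.23τ
- S = 6: √(50/885) = 0.24τ

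Simulation agrees (0.21, 0.23 and 0.24 for 3, 4 and 6 surgeons). With four surgeons, an assumed τ of 1, 3 or 5 minutes gives an error SD of 0.2, 0.7 or 1.1 minutes.

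**3. Scale.** The protocol cites a knee arthroplasty trial with an operating-time difference of 68.1 − 64.3 = 3.8 minutes, and a hip and knee study with a closure-time difference of 26.5 − 16.78 = 9.72 minutes. An error SD of 0.7 minutes is 0.7/3.8 = 18% of the first and 0.7/9.72 = 7% of the second.

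As a single bad draw, suppose one surgeon is 5 to 10 minutes slower (assumed) and is split 10:5. The shift is (10/30 − 5/30) × 5 to 10 = 0.8 to 1.7 minutes, or 22% to 44% of the 3.8-minute difference.

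**4. What adjustment can recover.** The information on the within-surgeon contrast, relative to an even split, is 4p(1 − p). At 2:1 it is 4 × (2/3) × (1/3) = 89%; at 7:3 it is 4 × 0.7 × 0.3 = 84%.

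**5. After the fix.** With permuted blocks of 4 within surgeon (an illustration), the arms differ by at most 2 patients for any surgeon: at worst 6:4 in 10 cases and 8:7 in 15.

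**The case against.** **The split percentages overstate harm.** They rise steeply as each surgeon has fewer cases, since 7:3 already counts at 10 cases. The error in the arm difference barely moves, from 0.18τ to 0.24τ. With two surgeons and a fixed 30:30 set, the risk of a 2:1 split is only 2%. This stands, and it is why the size of the problem is better stated as about 0.2 times the between-surgeon SD.

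**Randomization is valid, so this is not bias.** This stands too. A reader might infer that confounding by surgeon would invalidate the comparison. It would not: over repeated trials the imbalance averages to zero. The cost is lost precision, and this one trial carries whatever imbalance occurs.

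**Adjustment could deal with it.** A reader might infer that a surgeon who used mostly one suture makes later adjustment useless. At a 2:1 split that is wrong, since 89% of the information remains; only a near-total split blocks the comparison. The open-ended covariate list would allow surgeon to be added. But adjustment by surgeon needs surgeon to be recorded, and the plan does not list it.

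**A shared envelope set is not stated.** A reader might infer that one pooled set serves everyone. The section is silent on the number of sets; what can be said is that no stratification or blocking is described.

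**Several sites are not shown.** A reader might infer a multi-site trial from the regulatory sentence. No second site is named or counted, the background section says single-center, and one institution stores the data. The sentence may be generic. The wording still conflicts, but no argument about site effects should rest on it.

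**It is a pilot, and small strata are more predictable.** This is a fair caution when surgeons have few cases each. It bears on the choice of stratum and block size, and does not remove the gap.

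**Conclusion.** The point holds as a cheap improvement that should be made. Several surgeons take part, both primary endpoints depend on the operator, no stratification or blocking by surgeon is stated, surgeon identity is not listed for collection, and neither surgeon nor experience level is a named covariate. The result is avoidable chance error. It is modest against the cited closure-time difference and more noticeable against the cited 3.8-minute operating-time difference.

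These sizes rest on assumptions that the plan does not settle: the number of surgeons, equal caseloads, the between-surgeon SD and, for the main figures, a fixed 30:30 set. Simple randomization would give a higher chance of an uneven split. The documents do not support a finding of systematic bias, of a pooled envelope set, or of several sites actually taking part. The conflict over the number of sites is, by itself, a matter of wording.

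**What to change.** 1. In Randomization procedures, state the number of participating surgeons and prepare a separate 1:1 envelope set for each, in permuted blocks of varying size that is not disclosed to those who enrol or operate.
2. If there are many surgeons with few cases each, stratify by experience level instead. Its categories must then be defined and assigned before the envelope is drawn, because Table 1 now lists it only as an intra-operative item.
3. Add surgeon ID to Table 1 and record it for every case.
4. In Data Analysis, name the stratification factor as a term in the general linear model for closure time and for operative time.
5. Reconcile the single-center description with the regulatory sentence in both places where it appears. If there is more than one site, keep the envelope sets within site.

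The cost is re-packing envelopes, one data field and a few wording changes, with no added patients. The downside is slightly greater predictability within a surgeon, limited by varying the block size and not disclosing it.

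### The allocation envelope is drawn at the start of surgery although the arms differ only at the fascia; opening it just before closure would cheaply remove an avoidable route for bias into operative time.

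*Combined protocol and SAP*

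**What the plan says.** Under Randomization procedures, allocation is by sealed envelope in a 1:1 ratio: "At the commencement of each arthroplasty, a random envelope will be drawn which dictated the type of suture to be used". The purpose stated for this is "thus blinding the patients to the type of suture they received". No section mentions blinding the surgeon, theatre staff or a timekeeper, or says when the surgeon learns the arm.

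Study Design states that the primary endpoint "of the study will be closure time and operative time". The Background section puts the weight on one of the two: the study "will examine the outcomes, mainly closure time, of deep closure during total hip arthroplasty". Table 1 lists "Length of surgery time" and the length of closure as separate intra-operative items, but gives no start or stop point for either.

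Under Research Procedure, the active arm is described thus: "wound closure will be performed in this fashion: abductor muscles will be repaired using Ethibond 2-0". Then "STRATIFIX symmetric PDS Plus #1 will be used to close the fascia". Table 2, "Suture Type for Closure Following Total Hip Arthroplasty", has Muscle as its first row. The muscle, subcutaneous, subcuticular and skin rows are the same in both arms, and only the fascia row differs.

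**The concern.** Everything before the fascia is done in the same way, with the same materials, in both arms. The allocated suture has no means of changing how long it takes. If the surgeon knows the arm throughout, pace or staffing could still vary with it, and any such difference would pass straight into operative time and be read as an effect of the suture.

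Closure time may be exposed as well. Research Procedure treats muscle repair as part of wound closure. If the closure clock starts there, the clock includes a step in which the arms do not differ but the arm may already be known. Early knowledge could also influence who closes, which bears on closure time directly.

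The planned analysis would not correct this. Data Analysis names BMI, gender, age and ethnicity as covariates. Adjusting for baseline characteristics does not remove a shift caused by knowing the allocation.

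**Working it through.** The plan gives no figure to reproduce on this point: the 60 subjects are stated without an effect size, SD or power. The arithmetic below is for scale only.

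**Inputs from the documents**
- 60 subjects at 1:1, so 60/2 = 30 per arm (Sample; Randomization procedures).
- Two-sided testing at 0.05 (Data Analysis).
- Operative-time difference in the cited knee arthroplasty trial: 68.1 − 64.3 = 3.8 min, 250 per arm, p<0.001 (Background).

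**Assumptions**
- SD of operative time 10 to 15 min. The documents give none. The knee trial offers a rough anchor: with a common SD and a normal approximation, p<0.001 requires SD ≤ 3.8 / (3.29 × √(2/250)) ≈ 12.9 min. That is a different operation.
- Pre-closure shift b of 1, 2 or 4 min between arms, with no true suture effect.

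**Step 1: how often a pre-closure shift alone gives a significant result for operative time**

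Two-sample t test with 58 degrees of freedom, so the critical value is 2.0017. The standard error is SE = SD × √(2/30), and the noncentrality parameter is b/SE.
- SD 10: SE = 2.58 min. For b = 2, b/SE = 0.775.
- SD 15: SE = 3.87 min. For b = 2, b/SE = 0.516.

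| Shift b | SD 10 | SD 15 |
|---|---|---|
| 0 | 5.0% | 5.0% |
| 1 min | 6.7% | 5.7% |
| 2 min | 11.9% | 8.0% |
| 4 min | 33.2% | 17.4% |

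Simulation with 200,000 trials per cell agrees to within 0.1 percentage point. The 4-min row is extreme, since it exceeds the whole 3.8-min difference in the knee trial. A 2-min shift is 2/3.8 = 53% of that difference.

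**Step 2: whether the trial's own data could detect a shift afterwards**

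Table 1 allows surgery time minus closure time to be compared by arm. The 95% CI half-width is 2.0017 × SD × √(2/30) = 0.517 × SD, where SD is now that of time outside closure (assumed).

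| SD of non-closure time | Half-width | 2-min shift flagged | 4-min shift flagged |
|---|---|---|---|
| 5 min | 2.6 min | 33% | 86% |
| 10 min | 5.2 min | 12% | 33% |
| 15 min | 7.8 min | 8% | 17% |

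The check can reveal a large shift but cannot rule out a small one, so it does not replace later opening.

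**Step 3: effect of the change**

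If the arm is unknown until the pre-closure steps are finished, knowledge of it cannot alter their duration. Then b = 0 by this route, and it adds nothing to the nominal 5%. The sample size stays at 60.

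**The case against.** The strongest reply is that nothing here is shown to have gone wrong. Random allocation drawn after consent is sound and already limits selective enrolment. The text says the envelope is drawn; it does not say that the operating surgeon sees the content then, so surgeon knowledge is an inference. No passage supports a shift of even 1 or 2 min, and at 1 min the error rate barely moves. The study is a 60-subject pilot that puts closure time first. The surgeon must know the arm during fascial closure in any case, so bias there remains whatever is done about the envelope. Table 1 also records surgeon experience level, which partly allows a check on who closed.

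Most of this stands, and it limits the weight of the point. It does not remove the point. The inference is reasonable, because the envelope determines the suture and no one but the patient is said to be kept unaware. Unblinding during closure is unavoidable; unblinding before it is not. The one stated purpose of the procedure, patient blinding, is served equally well by later opening, as is allocation after consent. Surgeon experience level is recorded but is not among the named covariates, and recording it does not prevent an arm-driven choice of closer.

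**Conclusion.** The concern holds as a design improvement that should be made, with medium confidence. The plan allows the arm to be known during a part of surgery that the suture cannot affect but that, on any usual definition, counts in a primary endpoint. The exposure is mainly to operative time, and to closure time only if its clock starts at muscle repair or if early knowledge affects who closes.

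The size and direction of any bias are unknown. Under the assumed SDs of 10 to 15 min, shifts of 1 to 2 min would raise the false-positive rate for operative time from 5% to between about 6% and 12%. The conclusion does not depend on those figures. It rests on the order of the surgical steps, the identical materials outside the fascia, and the low cost of opening the envelope later.

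**What to change.** First define the start and stop of closure time, and say whether muscle repair falls inside it. Then replace the sentence on drawing the envelope with:

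> After implantation is complete, with the closing surgeon already recorded and immediately before the closure clock starts, the next sequentially numbered, opaque, sealed envelope will be opened by a team member who is not operating, and the patient ID and opening time will be logged.

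If closure time is defined to start at the fascia, the envelope should be opened after muscle repair and before that start.

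Add to Data Analysis:

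> Length of surgery minus length of closure will be reported by arm with a 95% confidence interval, as a check on time outside closure.

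The essential parts are the closure definition and the time of opening. The numbering, opacity and logging are ordinary envelope safeguards that can go into the same sentence.

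The cost is one definition, one replaced sentence and one analysis line using data already in Table 1, with no extra patients or visits. In theatre, both sutures stay on hand until closure, someone who is not operating must open and log the envelope, and the brief pause adds equally to operative time in both arms. If the envelope is opened before muscle repair, the arm is known during that step. Knowledge of the arm during fascial closure itself cannot be removed. Patient blinding is unchanged.
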